6.1.2 NONINVESTIGATIONAL MEDICINAL PRODUCT

6.1.2.1 Background medication

Metformin/Sulfonylurea

Participants are enrolled with a background therapy consisting of metformin alone or in combination with SU. Background metformin and SU are considered as NIMPs. Metformin and SU (commercial formulations) will be administered orally according to the locally approved label.

The dose of metformin, if taken as the only OAD, must be of ≥ 1500 mg/day (or as per country regulation if less) or maximum tolerated dose (maximum tolerated dose needs to be documented).

The dose of SU, if taken, must be at least half of maximum recommended dose according to national label. Participants are enrolled with their antidiabetic background therapy taken at a stable dose for at least 3 months prior to the Screening visit. Doses of metformin and, if applicable, SU should be kept stable throughout the study unless dose reduction is needed for safety reasons.

In participants with HbA1c $< 8\%$ at screening, the dose of SU is allowed to be decreased by at least 25% at randomization (according to investigator’s clinical judgment) in order to decrease the risk of hypoglycemia. For these patients, in case of uncontrolled SMPG values between Week 6 (Visit 6) and Week 12 (Visit 8), the SU dose can be progressively increased up to the Screening dose unless occurrence of hypoglycemia prevents this. Increasing the SU dose up to the screening dose level is not considered as rescue therapy.

In participants with HbA1c $\geq 8\%$ at screening, no SU dose adjustment is required at randomization.

Study participants, especially those on SU, must be educated to recognize and manage hypoglycemia. They also must be informed about the importance of adherence to dietary instructions (avoid deficient caloric intake). After randomization, once the double-blind study medication is added and increasingly contributing to the glucose-lowering activity, the risk of hypoglycemia may increase. In order to prevent hypoglycemia, a reduction of the SU dose might be considered in, for example in the following situations:

- Fasting (prebreakfast) SMPG below 100 mg/dL as a result of a consistently falling trend observed in the preceding 7 days
- Fasting (prebreakfast) SMPG below 80 mg/dL
- In case of 2 or more symptomatic or 1 severe hypoglycemic episode

6.1.2.2 Rescue Therapy

Rescue medication(s) that will be used to treat unacceptable hyperglycemia if a participant's glycemia reaches an applicable rescue threshold is considered NIMP for this study. The threshold values are defined in [Table 3](#), and are dependent on study period.

Table 3 - Rescue criteria

Time in study	Threshold
From randomization up through the scheduled Week 8 visit (Visit 7)	FPG >15.0 mmol/L (>270 mg/dL)
After the Week 8 visit up through the scheduled Week 12 visit (Visit 8)	FPG >13.3 mmol/L (>240 mg/dL)
After the Week 12 visit through the end of the 30-week treatment period	FPG >11.1 mmol/L (>200 mg/dL) or HbA1c ≥8.5%

FPG fasting plasma glucose; HbA1c hemoglobin A1c

Routine fasting SMPG and central laboratory alerts on FPG (and HbA1c from Week 12 [Visit 8] onwards) will be set up to ensure that glycemic parameter results remain below the predefined thresholds.

If a fasting SMPG value exceeds the specific glycemic limit on 1 day, the participant must check it again during the following 2 days. If all the SMPG values in 3 consecutive days exceed the specific limit, the participant should contact the Investigator and a central laboratory FPG measurement (and HbA1c from Week 12 onwards) be performed as soon as possible for confirmation.

Upon receipt of a central laboratory alert for either FPG or HbA1c, a central laboratory retest must be completed and confirmed as exceeding the threshold for rescue before rescue therapy is initiated. The retest confirmation should be performed as soon as possible during an unscheduled visit.

In the event that a confirmatory FPG and/or HbA1c value exceeds the threshold, the Investigator should ensure that no reasonable explanation exists for insufficient glucose control and in particular that:

- The increased FPG has been tested at a fasting status (ie, no food or liquid intake [except water] for ≥ 8 hours)
- IMP was given at the planned dose and was appropriately injected (as per weekly schedule)
- There was no intercurrent disease, which may jeopardize glycemic control (eg, infectious disease)
- Compliance to treatment was appropriate
- Compliance to diet and lifestyle was appropriate

If any of the above-mentioned explanations can reasonably explain the insufficient glycemic control, the Investigator should consider not initiating rescue medication(s) and should undertake appropriate action as follows, ie:

- Assess FPG (ie, after the participant has fasted for ≥ 8 hours)
- Initiate an evaluation and treatment of intercurrent disease (to be reported in the AE/concomitant medication parts of the electronic Case Report Form (eCRF) and the medical record)
- Stress the absolute need for the participant to be compliant with treatment
- Organize a specific interview with the participant and a Registered Dietician or other qualified nutrition professional to reinforce the absolute need to be compliant with diet and lifestyle recommendations, and schedule an FPG/HbA1c assessment at the next visit

If none of the above-mentioned reasons can be found, or if an appropriate action fails to decrease FPG/HbA1c below the threshold values, rescue medication(s) may be introduced.

If a participant needs to start rescue therapy, an unscheduled in-person visit will be scheduled to perform prerescue assessments (which are the same as those specified for EOT, Week 30, Visit 12) prior to starting the rescue medication(s).

Prescription of open-label rescue medication(s) to treat hyperglycemia will be at the discretion of the Investigator and in accordance with local standard of care and prescribing practice. With the exception of other GLP-1 RAs and DPP-4 inhibitors, any approved medications (including increase of prior metformin or SU dose) can be prescribed to treat the hyperglycemia. Increasing the SU dose up to the Screening dose level is not considered as rescue therapy in participants whose SU dose was temporarily decreased for HbA1c $< 8.0\%$ at Week -1 or for hypoglycemia.

If a participant requires glycemic rescue, the IMP received during the randomized, double-blind treatment period should be continued and must remain blinded until the end of the study (unless the Investigator considers a change necessary for safety reasons).

All concomitant antidiabetic medications (background OAD[s] and/or rescue therapy) will be documented in the eCRF.

The cost of NIMPs not covered by health insurance will be reimbursed by the study Sponsor where permitted by local regulations.

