6.3.1 Methods of blinding

During the entire double-blind treatment period, Investigators and participants will be blinded to the allocation of active or placebo treatment arms. Efpeglenatide and placebo will be provided in indistinguishable PFSs, in identical kits. Each titration and treatment kit (and the corresponding syringes) will be labeled with a unique number. The list of kit numbers will be generated by Sanofi.

In accordance with the double-blind design, Investigators will remain blinded to IMP and will not have access to the randomization (treatment) codes except under exceptional medical circumstances.

Members of the CEC will review and adjudicate events in a blinded manner (please also refer to Appendix 1 [[Section 10.1](#)]).

The Investigator will not have access to the data of the primary efficacy endpoint (ie, HbA1c) or FPG obtained after the baseline/randomization visit (Visit 3) as those data will be masked. If the central laboratory detects FPG greater than the rescue thresholds, the Investigator will receive an alert from the central laboratory (see [Section 6.1.2.2](#)). The HbA1c alerts will also be sent if a value is greater than the threshold from the Week 12 visit (Visit 8) onwards.

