8.1.5 Use of rescue therapy

The use of rescue medication(s) for hyperglycemia will be assessed and reported throughout the treatment period to allow determination of the start of rescue therapy and the percentage of participants using rescue therapy at Week 30. Routine fasting SMPGs will be measured by the participants, and alerts on FPG and/or HbA1c will be sent from the central laboratory to the Investigator to ensure that glycemic parameter results remain within predefined thresholds. For details and further actions should FPG and/or HbA1c values rise to values greater than the predefined thresholds, refer to [Section 6.1.2.2](#).

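### Table 3 sets HbA1c rescue at 8.5% or above, but the alert, retest and confirmation rules are worded as strictly above, so they miss a value of exactly 8.5%

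*Protocol*

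**What the plan says.** Protocol 6.1.2.2 refers the reader to Table 3 for the thresholds ("The threshold values are defined in" that table). For the period described as "After the Week 12 visit through the end of the 30-week treatment period", the entry is "FPG >11.1 mmol/L (>200 mg/dL) or HbA1c ≥8.5" percent. Every FPG criterion in the table uses a strict sign; HbA1c alone uses an inclusive one.

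Four other sentences refer to the same threshold:

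- Alert, Section 6.3.1: "The HbA1c alerts will also be sent if a value is greater than the threshold from the Week 12 visit (Visit 8) onwards".
- Retest, Section 6.1.2.2: after an alert, "a central laboratory retest must be completed and confirmed as exceeding the threshold for rescue before rescue therapy is initiated".
- Confirmation, Section 6.1.2.2: the investigator's next step begins "In the event that a confirmatory FPG and/or HbA1c value exceeds the threshold".
- Cross-reference, Section 8.1.5: the reader is sent back to 6.1.2.2 for what to do "should FPG and/or HbA1c values rise to values greater than the predefined thresholds".

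Section 6.3.1 and Appendix 2 (10.2) keep post-baseline HbA1c and FPG results from the sites.

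**The concern.** The definition and the rules that carry it out use different operators for HbA1c. A laboratory flag has to be programmed with one of them. Because the result is masked, that flag decides whether the investigator learns that the HbA1c criterion has been met. The retest is a second gate, since rescue may not start until it is confirmed, and it has the same mismatch.

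What is at stake is a participant-protection rule at one boundary value. As the protocol was designed, two exploratory endpoints also depend on it: the number of participants given rescue therapy and the time to its initiation (Protocol Section 3, Table 1).

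**Working it through.** The plan gives no figure to reproduce here, so the first check applies each rule, as worded, to three HbA1c values.

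| HbA1c | Table 3 (≥8.5%) | Alert, 6.3.1 (>) | Retest and confirmation, 6.1.2.2 (>) |
|---|---|---|---|
| 8.4% | not met | no alert | not confirmed |
| 8.5% | met | no alert | not confirmed |
| 8.6% | met | alert | confirmed |

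The rules disagree only at exactly 8.5%. There are two routes to the conflict: a first reading of 8.5% that raises no alert, and a higher first reading that raises an alert but is followed by a retest of 8.5%, which does not exceed the threshold.

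**Does other wording settle the operator?** Sections 2.3, 6 and 6.1.2.2 also speak of values reaching a threshold, or of keeping them under or below it. That fits an inclusive limit, but the same sentences cover FPG, which Table 3 sets as strict, so they do not decide the matter. No sentence says that exceeding includes equality. Table 3 governs because it is the stated definition.

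**Which samples are in scope?** The Schedule of Activities has HbA1c at Visits 1, 3, 8 (Week 12) and 11 (Week 30). Table 3 applies HbA1c only after the Week 12 visit. The Week 12 sample therefore comes in only through the alert wording, "central laboratory alerts on FPG (and HbA1c from Week 12 [Visit 8] onwards". Otherwise the one scheduled sample in scope is Week 30, at end of treatment, plus retests and tests prompted by self-monitored glucose.

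**How often might a reading equal 8.5%?** The documents do not give the distribution of post-baseline HbA1c or its reporting precision. The SD of 1.1% in Section 9.2 is for change from baseline, so it does not supply this. Assume one normal reading with mean m from 7.0% to 8.6% and SD s of 0.8 or 1.1.

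- Reported to 0.1%: P = Φ((8.55 − m)/s) − Φ((8.45 − m)/s).
- Reported to 0.01%: P = Φ((8.505 − m)/s) − Φ((8.495 − m)/s).

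For example, with m = 8.0 and s = 0.8 at 0.1% precision, P = Φ(0.6875) − Φ(0.5625) = 4.10%.

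| Mean | To 0.1%, SD 0.8 | To 0.1%, SD 1.1 | To 0.01%, SD 0.8 | To 0.01%, SD 1.1 |
|---|---|---|---|---|
| 7.0 | 0.86% | 1.43% | 0.086% | 0.143% |
| 7.5 | 2.28% | 2.40% | 0.228% | 0.240% |
| 8.0 | 4.10% | 3.27% | 0.410% | 0.327% |
| 8.5 | 4.98% | 3.63% | 0.499% | 0.363% |
| 8.6 | 4.94% | 3.61% | 0.495% | 0.361% |

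The upper ends need a mean at or near 8.5%. These are shares of readings, not lost rescues: a lost rescue would also need no FPG trigger and an investigator who would have chosen to treat.

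**The case against.** The strongest reply is that this is a copy-edit. Three of the four strict sentences (retest, confirmation and 8.1.5) are shared with FPG, so they settle the HbA1c operator no better than the inclusive wording does. That leaves one HbA1c-specific sentence, in a section about blinding. The threshold column of Table 3 also contains the operator itself, so exceeding the threshold can be read as meeting that entry. Finally, Table 3 defines the rescue criterion, not the laboratory flag, and the flag specification is not in the documents.

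Much of this stands. The shared sentences are weak evidence of intent, the loose reading is available, and nobody can tell from the documents whether an 8.5% would in fact have gone unflagged, or whether the site sees the retest value or only a flag. It does not remove the conflict. The alert sentence is specifically about HbA1c and uses a plain operator that could be copied into an alert specification. The shared sentences, whatever was intended, still apply to HbA1c as worded. The site cannot correct the matter by looking at the value.

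The objection that nothing in the analysis changes is also right. The protocol's primary analysis uses HbA1c regardless of rescue (Section 9.4.1, Table 5). SAP 1.6 drops the planned efficacy evaluations after early termination, and SAP 2.4 and 2.4.3 summarise only HbA1c, FPG, body weight and the 7% responders.

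**Conclusion.** The concern holds, at minor severity. As written, the alert, retest and confirmation rules do not carry out Table 3 at an HbA1c of exactly 8.5%. That conclusion rests on the wording alone and is firm. Its practical effect is small and cannot be quantified from the documents; the probabilities above depend entirely on an assumed mean, SD and reporting precision. Few scheduled HbA1c samples are in scope, FPG and self-monitored glucose triggers remain active, and 6.1.2.2 leaves the start of rescue to the investigator. No sample size, power, primary analysis or SAP analysis is affected. With the trial ended, the correction serves the protocol record and any reuse of this rescue wording.

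**What to change.** Keep Table 3 at 8.5% or above. In Section 6.3.1, in the retest and confirmation sentences of 6.1.2.2, and in 8.1.5, change the HbA1c wording to *meets the Table 3 rescue criterion*. Leave FPG as strictly greater. Confirm that the central-laboratory HbA1c flag fires at 8.5% and above.

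Changing Table 3 to strictly above 8.5% would also remove the conflict, but it would alter the stated criterion.

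The cost is a few words in three sections and one check of the laboratory alert specification.

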6.2 PREPARATION/HANDLING/STORAGE/ACCOUNTABILITY

Investigators or other authorized persons (eg, pharmacists) are responsible for storing the IMP in a secure and safe place in accordance with local regulations, labeling specifications, policies, and procedures.

Control of IMP storage conditions, especially control of temperature (eg, refrigerated storage) and information on in-use stability and instructions for handling the Sanofi compound should be managed according to the rules provided by the Sponsor.

The expiry date is mentioned on the IMP labels (when required by country regulation), and storage conditions are written on the IMP labels and in the instruction leaflet.

The Investigator or designee must confirm appropriate temperature conditions have been maintained during transit for all study IMP received and any discrepancies are reported and resolved before use of the study intervention.

Only participants enrolled in the study may receive study intervention and only authorized site staff may supply or administer study IMP. All study IMP must be stored in a secure, environmentally controlled, and monitored (manual or automated) area in accordance with the labeled storage conditions with access limited to the Investigator and authorized site staff.

The Investigator, institution, or the head of the medical institution (where applicable) is responsible for study IMP accountability, reconciliation, and record maintenance (ie, receipt, reconciliation, and final disposition records).

Further guidance and information for the final disposition of unused study IMP are provided in separate study document.

The Investigator, the hospital pharmacist, or other personnel allowed to store and dispense the IMP will be responsible for ensuring that the IMP used in the clinical trial is securely maintained as specified by the Sponsor and in accordance with applicable regulatory requirements. All IMPs will be dispensed in accordance with the Investigator's prescription and it is the Investigator's responsibility to ensure that an accurate record of IMP issued and returned is maintained.

Any quality issue noticed with the receipt or use of an IMP/NIMP/device (deficiency in conditions, appearance, pertaining documentation, labeling, expiration date, etc) must be promptly notified to the Sponsor. Some deficiencies may be recorded through a complaint procedure (see [Section 8.3.8](#)).

A potential defect in the quality of IMP/NIMP/device may be subject to initiation of a recall procedure by the Sponsor. In this case, the Investigator will be responsible for promptly addressing any request made by the Sponsor, in order to recall the IMP/NIMP/device and eliminate potential hazards.

Under no circumstances will the Investigator supply IMP/NIMP/device to a third party, allow the IMP/NIMP/device to be used other than as directed by this clinical trial protocol, or dispose of IMP/NIMP/device in any other manner.

6.3 MEASURES TO MINIMIZE BIAS: RANDOMIZATION AND BLINDING

All participants will be centrally assigned to randomized study IMP using interactive response technology (IRT) as summarized in the SoA ([Section 1.3](#)). Before the study is initiated, instructions on how to access IRT will be provided to each site.

A randomized participant is a participant who has been randomly allocated to a study IMP, regardless whether the IMP kit was used or not. A participant cannot be randomly assigned more than once in the study.

Returned study IMP should not be redispensed to the participants.

6.3.1 Methods of blinding

During the entire double-blind treatment period, Investigators and participants will be blinded to the allocation of active or placebo treatment arms. Efpeglenatide and placebo will be provided in indistinguishable PFSs, in identical kits. Each titration and treatment kit (and the corresponding syringes) will be labeled with a unique number. The list of kit numbers will be generated by Sanofi.

In accordance with the double-blind design, Investigators will remain blinded to IMP and will not have access to the randomization (treatment) codes except under exceptional medical circumstances.

Members of the CEC will review and adjudicate events in a blinded manner (please also refer to Appendix 1 [[Section 10.1](#)]).

The Investigator will not have access to the data of the primary efficacy endpoint (ie, HbA1c) or FPG obtained after the baseline/randomization visit (Visit 3) as those data will be masked. If the central laboratory detects FPG greater than the rescue thresholds, the Investigator will receive an alert from the central laboratory (see [Section 6.1.2.2](#)). The HbA1c alerts will also be sent if a value is greater than the threshold from the Week 12 visit (Visit 8) onwards.

6.3.2 Randomization code breaking during the study

The blind may be broken if, in the opinion of the Investigator, it is in the participant's best interest for the Investigator to know the IMP assignment. The Sponsor must be notified before the blind is broken unless identification of the IMP is required for a medical emergency in which the knowledge of the specific blinded study treatment will affect the immediate management of the participant's conditions (eg, antidote available). In this case, the Sponsor must be notified within 24 hours after breaking the blind. The date and reason that the blind was broken must be recorded in the source documentation and eCRF, as applicable.

Code breaking can be performed at any time by using the proper module of the IRT and/or by calling any other phone number provided by the Sponsor for that purpose. If the blind is broken, the Investigator should document the date, time of day and reason for code breaking. If the code is broken by the Investigator, the participant must withdraw from IMP administration. When documenting the reason for unblinding, the Investigator must not provide any detail regarding the nature of the IMP. The Investigator should not divulge IMP details to the Sponsor's representative or to any staff members until database closure. Furthermore, when completing forms (eg, AE, SAE, adjudication information), the study treatment should not be disclosed on the forms.

Randomization code breaking will also be performed during the analysis of the PK serum concentration samples and ADA samples in order to enable the laboratory to sort the samples (verum [dose group], placebo) and start analyzing the samples (verum group only) while the study is still ongoing. Only the Project Manager and lead scientist at the Bioanalytical laboratory, as well as the popPK analyst, will have access to the randomization code to allow for the sorting of the epeglenatide blood samples. The Bioanalytical laboratory and responsible personnel will follow the standard procedures to ensure the protection of the blind within the Sponsor's clinical team. The randomization code or the individual analytical results will not be disclosed to any clinical team personnel prior to the database lock.

The DMC will receive unblinded safety data from an independent statistician for review, which will be handled strictly confidentially. None of these reports may be delivered to unauthorized persons (Appendix 1 [[Section 10.1](#)]).

Refer to [Section 8.3.4](#) for suspected unexpected serious adverse reaction (SUSAR) unblinding by the Sponsor.

6.4 STUDY INTERVENTION COMPLIANCE

Measures taken to ensure and document treatment compliance and IMP/NIMP accountability include the following:

- Proper recording of treatment kit number as required on appropriate eCRF page for accounting purposes
- All medication treatment kits (whether empty or unused) will be returned by the participant at each visit when treatment dispensing is planned

- The Investigator or his/her delegate will track treatment accountability/compliance by comparing the treatment kit number recorded on the patient diary with the treatment kit number of returned treatment kits (whether empty or unused) and completes the participant treatment log
- The monitor in charge of the study will then check the data entered on the IMPs administration page of the eCRF by comparing them with the IMPs that have been retrieved and the participant treatment log form
- For the NIMP not provided by the Sponsor, tracking and reconciliation will be documented in participant's source documents and medication reported in appropriate eCRF pages

